9.3.2. Analyses of Subgroups/additional Analyses

9.3.2.1. Therapeutic Pathway of Patient

9.3.2.1.1. Targeted Therapy

Table 14.2.2.2.1.1: Number of Patients with Targeted Therapy – Reference Set – Analysis of the Period before Inclusion

		Total (N=XX)
Number of patients having received at least one targeted therapy before inclusion		XX (XX.X%)
Number of patients having received Everolimus at least once before inclusion		XX (XX.X%)
Number of patients having received Sunitinib at least once before inclusion		XX (XX.X%)
Number of patients having received Pazopanib at least once before inclusion		XX (XX.X%)
Number of patients having received Everolimus at least once and Sunitinib at least once before inclusion		XX (XX.X%)
Number of patients having received Everolimus at least once but not Sunitinib or Pazopanib before inclusion		XX (XX.X%)
Number of patients having received Sunitinib at least once but not Everolimus or Pazopanib before inclusion		XX (XX.X%)
Number of patients who never received targeted therapy before inclusion		XX (XX.X%)
Number of targeted therapies received per patient before inclusion	N Missing data Mean (SD) Mean [Min; Max] [Q1; Q3]	XX XX XX.XX (X.XX) XX.X [XX.X; XX.X] [XX.X; XX.X]
	0 1 2 3 >3	XX (XX.X%) XX (XX.X%) XX (XX.X%) XX (XX.X%) XX (XX.X%)
Number of patients having received two different targeted therapies* before inclusion		XX (XX.X%)

^{*} Two different targeted therapies: Everolimus and Sunitinib, or Everolimus and Pazopanib, or Sunitinib and Pazopanib.

Using the same template:

Table 14.2.2.2.1.2: Number of Patients with Targeted Therapy – Reference Set – Analysis of the Period at Inclusion and after Inclusion

Table 14.2.2.2.1.3: Number of Patients with Targeted Therapy – Reference Set – Analysis of the Overall Follow-Up Period

Table 14.2.2.2.1.4: Position of the Targeted Therapy in the Care Pathway of Patients Throughout Follow-Up – Reference Set

	Total (N=XX)
Number of patients having received a targeted therapy as the 1st main treatment line	XX (XX.X%)
Number of patients having received a targeted therapy as the 2nd main treatment line	XX (XX.X%)
Number of patients having received a targeted therapy as the main treatment line	XX (XX.X%)
Number of patients having received a targeted therapy as the nth main treatment line	XX (XX.X%)
Number of patients having received a targeted therapy immediately before chemotherapy	XX (XX.X%)
Number of patients having received a targeted therapy immediately after chemotherapy	XX (XX.X%)
Number of patients having received a targeted therapy immediately before a somatostatin analoganalog (as main treatment)	XX (XX.X%)
Number of patients having received a targeted therapy immediately after a somatostatin analoganalog (as main treatment)	XX (XX.X%)

Programmer note: add as a footnote the list of patients whose start date for their last main treatment line falls after the date of the last visit.

Table 14.2.2.2.1.5: Length and Reason for Discontinuation of Targeted Therapy

- Reference Set - Analysis of the Period before Inclusion

		Total
		(N=XX)
Length of targeted therapy before inclusion (months) (1)	N	XX
	Missing data	XX
	Mean (SD)	XX.XX (X.XX)
	Mean	XX.X
	[Min; Max]	[XX.X; XX.X]
	[Q1; Q3]	[XX.X; XX.X]
Length of Everolimus targeted therapy before inclusion (months) (1)	N	XX
	Missing data	XX
	Mean (SD)	XX.XX (X.XX)
	Mean	XX.X
	[Min; Max]	[XX.X; XX.X]
	[Q1; Q3]	[XX.X; XX.X]
Length of Sunitinib targeted therapy before	N	XX
inclusion (months) (1)	Missing data	XX
	Mean (SD)	
	Mean	XX.XX (X.XX)
		XX.X
	[Min; Max]	[XX.X; XX.X]
	[Q1; Q3]	[XX.X; XX.X]
Reason for discontinuation of targeted therapy before inclusion (2)	N	XX
	Missing data	XX
	Adverse event*	XX (XX.X%)
	Progression	XX (XX.X%)
	Planned discontinuation of	XX (XX.X%)
	treatment	727 (777.7770)
	Patient decision	VV (VV V0/.)
		XX (XX.X%)
	Other	XX (XX.X%)
Reason for discontinuation of Everolimus targeted therapy before inclusion (2)	N	XX
	Missing data	XX
	Adverse event*	XX (XX.X%)
	Progression	XX (XX.X%)
	Planned discontinuation of	XX (XX.X%)
	treatment	
	Patient decision	XX (XX.X%)
	Other	XX (XX.X%)
Reason for discontinuation of Sunitinib targeted therapy before inclusion (2)	N	XX
2 17 (-/	Missing data	XX
	Adverse event*	XX (XX.X%)
	Progression	XX (XX.X%)
	Planned discontinuation of	
	treatment	XX (XX.X%)
	Patient decision	XX (XX.X%)
	Other	XX (XX.X%)
		()

^{*} The "Total" column shows all of the targeted therapies.

⁽¹⁾ Data reported directly from the e-CRF, total of data if several targeted therapies.

⁽²⁾ The number of reasons for discontinuation will be higher than the set having received targeted therapy (ie, patients having discontinued Everolimus and Sunitinib).

⁽³⁾ Total duration representing the entire follow-up period (before and after inclusion).

Using the same template:

Table 14.2.2.2.1.6: Length and Reason for Discontinuation of Targeted Therapy in the Care Pathway of Patients – Reference Set – Analysis of the Period before and after Inclusion

Table 14.2.2.2.1.7: Length and Reason for Discontinuation of Targeted Therapy in the Care Pathway of Patients – Reference Set – Analysis of the Entire Follow-Up Period

Table 14.2.2.2.1.8: Length and Reason for Discontinuation of Targeted Therapy

- Reference Set - Subgroup Analysis Based on the Number of Main Treatment

Line Throughout Follow-Up

		1 st Line (N=XX)	2 nd Line (N=XX)	 (N=XX)	N th Line (N=XX)
Length of targeted therapy (months)	N	XX	XX	XX	XX
)	Missing data	XX	XX	XX	XX
	Mean (SD) Mean	XX.XX (X.XX) XX.X	XX.XX (X.XX) XX.X	XX.XX (X.XX) XX.X	XX.XX (X.XX) XX.X
	[Min; Max] [Q1; Q3]	[XX.X; XX.X] [XX.X; XX.X]	[XX.X; XX.X] [XX.X; XX.X]	[XX.X; XX.X] [XX.X; XX.X]	[XX.X; XX.X] [XX.X; XX.X]
Reason for discontinuation of targeted therapy	N	XX	XX	XX	XX XX
0 17	Missing data	XX	XX	XX	
	Adverse event*	XX (XX.X%)	XX (XX.X%)	XX (XX.X%)	XX (XX.X%)
	Progression	XX (XX.X%)	XX (XX.X%)	XX (XX.X%)	XX (XX.X%)
	Planned discontinuation of treatment	XX (XX.X%)	XX (XX.X%)	XX (XX.X%)	XX (XX.X%)
	Patient decision	XX (XX.X%)	XX (XX.X%)	XX (XX.X%)	XX (XX.X%)
	Other	XX (XX.X%)	XX (XX.X%)	XX (XX.X%)	XX (XX.X%)

Using the same template:

Table 14.2.2.2.1.9: Length and Reason for Discontinuation of Targeted Therapy Over the Entire Follow-Up Period – Reference Set – Subgroup Analysis Based on the Number of Main Treatment Lines Throughout Follow-Up (≤2 Lines, >2 Lines)

Table 14.2.2.2.1.10: Length and Reason for Discontinuation of Targeted Therapy Over the Entire Follow-Up Period − Reference Set − Subgroup Analysis Based on the Ki67 (≤10%, >10%)

Table 14.2.2.2.1.11: Length and Reason for Discontinuation of Targeted Therapy Over the Entire Follow-Up Period – Reference Set – Subgroup Analysis Based on the Percentage of Liver Invasion (≤50%, >50%)

Table 14.2.2.2.1.12: Length and Reason for Discontinuation of Targeted Therapy Over the Entire Follow-Up Period – Reference Set – Subgroup Analysis Based on the Number of Metastatic Sites at Initiation of the Current Treatment Line or Treatment Line Started at Inclusion (≤2 Sites, >2 Sites)

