- Number of right censors (with details of patients who are lost to follow-up, no disease progression/death);
- Survival (in months): median (+95% CI), Q1 (+95% CI), Q3 (+95% CI), minimum, maximum;
- Estimated survival rate at a specific time (for example 6 months, 1 year and 2 years): number of subjects at risk, survival rate at each time.

These survival rates will be estimated and described in each of the following groups and subgroups:

- Targeted therapies group (with an estimate in the Everolimus and Sunitinib subgroups);
- Other treatments group (with an estimate in the chemotherapy, somatostatin analogs, interferon alpha and metabolic radiotherapy subgroups).

Handling of truncation/left censoring:

The study includes a retrospective and/or prospective data collection period depending on whether the patient is prevalent or incident in terms of his/her tumour treatment at the time of inclusion into the study.

The time to event of interest ("survival" time) or censoring if no event occurs (right censoring) will be based on the treatment line start date at the time the patient was included into the study.

As a result, when patients are recruited into the study, those patients who have already died on treatment could not be included, whereas patients who were still alive on treatment were included. This is left truncation.

In addition, the prevalent patients included could progress before inclusion into the study and not stop the treatment started or ongoing at the time of inclusion. This progression could not be identified and is a left censoring.

In practice, after disease progression on a given treatment, the treatment is changed. As a result, prevalent patients we observed on a given treatment at inclusion could not by definition experience disease progression.

As a result, we also do not see patients on a given treatment at inclusion who progressed on the same treatment prior to entering the study and we therefore deem these cases to be left truncations.

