5.9.3. Therapeutic Pathway of Patient

The therapeutic pathway of the patient will be described based on the three treatments (main treatment line: Targeted therapy, Chemotherapy and Somatostatin analogs).

Targeted therapy

The targeted therapy will be described for each period (overall follow-up, before inclusion, after inclusion) and as follows:

- Number of patients having received at least one targeted therapy.
- Number of patients having received Everolimus at least once.
- Number of patients having received Sunitinib at least once.
- Number of patients having received Pazopanib at least once.
- Number of patients having received Everolimus at least once and Sunitinib at least once.
- Number of patients having received Everolimus at least once, but not Sunitinib or Pazopanib.
- Number of patients having received Sunitinib at least once, but not Everolimus or Pazopanib.
- Number of patients who never received targeted therapy.
- Number of targeted therapies received per patient (quantitative and by class: 0 / 1 / 2 / 3 / 4 and more).

Targeted therapy will be described for the entire follow-up based on:

• Number of patients having received two different targeted therapies (Everolimus and Sunitinib, or Everolimus and Pazopanib).

In addition, the position of the targeted therapy in the care pathway of the patient will be described for the entire follow-up:

- Number of patients having received a targeted therapy as the 1st, 2nd, 3rd, nth main treatment line.
- Number of patients having received a targeted therapy immediately before/after chemotherapy.
- Number of patients having received a targeted therapy immediately before/after a somatostatin analog (as main treatment).

The duration of the targeted therapy (in months) and reasons for the discontinuation will also be described irrespective of the targeted therapy and by differentiating between Everolimus and Sunitinib during the period before inclusion then after inclusion.

The total duration of the targeted therapy (obtained by adding the periods before inclusion and after inclusion) will be described.

The analysis and duration of the targeted therapy (irrespective of the targeted therapy) and the reasons for the discontinuation will also be presented based on the following subgroups:

- Main treatment lines during follow-up (1/2/.../n).
- Number of patients with ≤ 2 lines, ≥ 2 main treatment lines for the entire follow-up.
- Ki67 (the most recent prior to inclusion) ($\leq 10\% / > 10\%$).

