5.9.6. Main Treatment Lines Received Over the Entire Follow-up Period

For each main treatment line, the number of main treatment lines, the nature of treatments, the duration and reasons for discontinuation will be presented over the entire follow-up (retrospective phase and prospective phase) overall and based on the current treatment at inclusion (targeted therapy/ chemotherapy / somatostatin analog).

The number of main treatment lines received during the study (quantitative and by class), the nature of lines of treatment received during the study (other than those received at inclusion) and the total number of treatment lines received will be shown based on the "at least one targeted therapy before inclusion (yes /no)" subgroup.

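### Length of targeted therapy and reason for stopping are split by total main lines over follow-up, a count that for line-1 and line-2 therapies partly results from when the therapy stopped

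*SAP*

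**What the plan says.** SAP 5.9.3 states that the duration of targeted therapy and the "reasons for the discontinuation will also be presented based on the following subgroups". One of those subgroups is the number of "main treatment lines for the entire follow-up", cut at two lines. The table shell in SAP 9.3.2.1.1 carries the same split: "Subgroup Analysis Based on the Number of Main Treatment Lines Throughout Follow-Up (≤2 Lines, >2 Lines".

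Four other statements determine what that split means:

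- **Period.** SAP 5.9.6 describes main lines "over the entire follow-up (retrospective phase and prospective phase"), so lines given before inclusion count. Patients may be included on line 1, 2, 3 or 4 (SAP 3.3).
- **Line.** Under SAP 4.7 each new treatment opens a new main line.
- **What ends a line.** SAP 5.5.1 says: "In practice, after disease progression on a given treatment, the treatment is changed".
- **Length.** SAP 5.9.3: "The total duration of the targeted therapy (obtained by adding the periods before inclusion and after inclusion) will be described". Footnotes under Table 14.2.2.2.1.5 add "Data reported directly from the e-CRF, total of data if several targeted therapies" and "Total duration representing the entire follow-up period (before and after inclusion"). The shell used for Tables 14.2.2.2.1.8 and 14.2.2.2.1.9 does not repeat these footnotes, so summing in the challenged table is the natural reading but is not spelled out.

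Neither SAP 5.9.3 nor the limitations in SAP section 6 warns that this grouping depends on the outcome, and no landmark or time-dependent handling is described for it.

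**The concern.** A grouping variable for a duration should be fixed before the duration is observed. Here it is not. A patient on a line-2 targeted therapy stays in the ≤2 group while that therapy continues, and moves to >2 only when it ends and another treatment begins. Long therapy keeps the patient in ≤2; early stopping followed by a switch moves the patient to >2. The rows for reason for stopping are affected too, because patients still on therapy have no reason to report and are unevenly spread over the two groups.

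The columns stand side by side in a study done at the request of the health authority to describe targeted therapies in practice. A reader may take them to say that targeted therapy lasts longer, or ends for different reasons, in patients who need fewer lines. The display cannot support that reading.

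**Working it through.** **The plan's own figures.** No figure is stated for this table. The plan's sizing precision (SAP 4.2) reproduces, 1.96 × √(0.25/150) = 0.080 and 1.96 × √(0.25/75) = 0.113, but does not bear on this point.

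**Who can be sorted by duration.** The count equals lines before the targeted therapy, plus that therapy, plus later lines.

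- Targeted therapy on line 1: >2 only if it ends and at least two further lines start.
- Targeted therapy on line 2: >2 as soon as it ends and one further line starts.
- Inclusion on line 3 or 4: always >2.

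**Illustration 1, closed form.** Assumptions, none from the documents except the 24 months of prospective follow-up: all patients are incident on a line-2 targeted therapy; duration is exponential with mean 12 months, the same for everyone; each stop is followed at once by a new line.

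Without deaths:

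- ≤2 requires duration ≥24 months: probability e^(-24/12) = 0.135, observed length 24.0 months.
- >2: mean of the exponential truncated at 24 = 12 − 24 × 0.1353/(1 − 0.1353) = 8.2 months.

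With 70% two-year overall survival, constant hazard and independent of treatment:

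- Death hazard = −ln(0.70)/24 = 0.01486 per month; total hazard = 1/12 + 0.01486 = 0.09819.
- Still on therapy at 24 months: 0.70 × e^(-2) = 0.0947.
- Died on therapy: (0.01486/0.09819) × (1 − 0.0947) = 0.137.
- Mean length if the therapy ended before 24 months: 1/0.09819 − 24 × 0.0947/0.9053 = 7.7 months. This is the >2 mean.
- ≤2 mean: (0.0947 × 24 + 0.137 × 7.67)/(0.0947 + 0.137) = 14.3 months.

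So identical patients give 24.0 vs 8.2, or 14.3 vs 7.7.

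**Illustration 2, simulation with mixed lines.** 200,000 patients per scenario, all with the same targeted-therapy duration distribution. Assumptions not in the documents: exponential durations; median 11 months for targeted therapy (8 and 16 also tried for the inclusion therapy alone) and 8 months for other therapy; 40% prevalent with 0 to 12 months already elapsed; each stop opens a new line; no deaths. Chance of another targeted therapy: 20% per earlier line and 30% for the next (low), or 40% and 50% (high).

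Length summed over all targeted therapies, months:

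| Line at inclusion (1/2/3/4) | Chance of another targeted therapy | ≤2 | >2 | Gap |
|---|---|---|---|---|
| 50/30/15/5% | low | 23.98 | 17.10 | +6.88 |
| 50/30/15/5% | high | 25.54 | 21.94 | +3.60 |
| 25% each | low | 24.67 | 20.99 | +3.68 |
| 25% each | high | 26.35 | 28.18 | −1.83 |
| 10/30/35/25% | low | 26.49 | 21.92 | +4.57 |
| 10/30/35/25% | high | 28.75 | 29.50 | −0.75 |

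If everyone enters on line 1, the summed gap is about +11 months. If only the inclusion therapy is counted, the gap is +8.0 to +11.7 months over all line mixes and medians tried, and about 9 to 16 months within patients included on line 1 or on line 2. In those runs 32 to 84% of the ≤2 group were still on therapy at the end and so had no reason for stopping, against 0 to 26% of the >2 group.

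**How much of the count is duration.** In the mixed-line scenarios, duration of the inclusion therapy accounts for about 20 to 34% of the variance in line count, and line at inclusion for about 27 to 39%.

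**The case against.** The best defence has four parts.

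- **The count has other sources.** It includes up to three lines before inclusion. Under SAP 4.7 it also rises with locoregional treatment during the study and with the same drug resumed after more than three months. The case report form also allows treatment abstention after a stop, so a stop need not lead to a new line. This stands. A reader might infer that the line count is largely fixed by how long the therapy lasted; the documents support only a partial dependence, confined to line-1 and line-2 therapies.
- **No stable direction.** Summing over several targeted therapies adds time to the >2 group. A reader might infer from 24.0 vs 8.2 that the table must favour ≤2. It need not: that case is extreme, with only 13.5% of patients in ≤2, all at the 24-month ceiling. An unpredictable sign does not rescue the table, however, since it leaves the contrast without a usable meaning.
- **Reasons for stopping.** A reader might infer that deaths on treatment will pile up as a stop reason under ≤2. The shell has no row for death or for ongoing therapy; its rows are adverse event, progression, planned stop, patient decision and other. What remains is that these rows rest on selected patients.
- **Descriptive, and largely shown elsewhere.** The title does say throughout follow-up, no test is planned, and Table 14.2.2.2.1.8 already gives the same outcomes in columns by ordinal line. This limits the harm and makes the change cheap, but it leaves the outcome-dependent split in the plan without a caveat. The SAP's warning against comparisons (6.4) concerns treatment groups, not this grouping.

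**Conclusion.** The concern holds in a limited form. For patients whose targeted therapy is on line 1 or 2, the ≤2 vs >2 grouping partly depends on the outcome being tabulated; patients included on line 3 or 4 are placed in >2 regardless. The table thus mixes line position with a consequence of duration, and a difference between its columns cannot be attributed to the number of lines.

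The size cannot be given for this study. It depends on the line mix at inclusion, mortality, line durations and the summing rule, and the documents supply no values for the first three. The figures above show only what identical patients can produce, from a large positive gap to a small negative one. No primary or stated secondary conclusion rests on this table, but it should be changed before it is reported.

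**What to change.** In Table 14.2.2.2.1.9 and the matching bullet of SAP 5.9.3, define the two groups by the line position at which the targeted therapy was started (≤2 vs >2). Use one record per targeted-therapy line and do not sum lengths across therapies. Position is known before the outcome and needs no new data: it underlies the ordinal columns of Table 14.2.2.2.1.8 (read here as line position) and is reported in Table 14.2.2.2.1.4. SAP 5.9.7 already treats line number at inclusion and total lines over follow-up as separate variables. While editing, confirm that the cut-off in SAP 5.9.3 is ≤2 vs >2, as in the table title; the available text shows overlapping signs there, possibly a reading error from the PDF.

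If the total-lines split is kept, add a footnote that the groups depend on treatment duration and must not be contrasted, and refer the reader to Table 14.2.2.2.1.8.

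The cost is a wording change and one re-cut descriptive table. The drawback is that a patient with two targeted therapies can appear in both groups, which the footnote should state. The same total-lines split is used in Tables 14.2.2.4.1 and 14.2.2.6.20; these were not quantified here but should be looked at together with this one.

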9.3.2.1.2. Chemotherapy

Table 14.2.2.2.1: Number of Chemotherapy Patients – Reference Set – Analysis of the Period before Inclusion

		Total (N=XX)
Number of patients having received chemotherapy at least once before inclusion		XX (XX.X%)
Number of patients who never received chemotherapy before inclusion		XX (XX.X%)
Number of chemotherapies received per patient before inclusion	Missing data Mean (SD) Mean [Min; Max] [Q1; Q3]	XX XX XX.XX (X.XX) XX.X [XX.X; XX.X] [XX.X; XX.X]
	0 1 2 3 >3	XX (XX.X%) XX (XX.X%) XX (XX.X%) XX (XX.X%) XX (XX.X%)
Number of patients having received chemotherapy and a somatostatin analoganalog as main treatment before inclusion	ı	XX (XX.X%)

Using the same template:

Table 14.2.2.2.2: Number of Chemotherapy Patients – Reference Set – Analysis of the Period at Inclusion and after Inclusion

Table 14.2.2.2.2: Number of Chemotherapy Patients – Reference Set – Analysis of the Overall Follow-Up Period

Table 14.2.2.2.4: Position of Chemotherapy in the Care Pathway of Patients for the Entire Follow-Up – Reference Set –

		Total (N=XX)
Number of patients having received chemotherapy as the 1st main treatment line		XX (XX.X%)
Number of patients having received chemotherapy as the 2nd main treatment line		XX (XX.X%)
Number of patients having received chemotherapy as thenth main treatment line		XX (XX.X%)
Number of patients having received chemotherapy as the nth main treatment line		XX (XX.X%)
Number of patients having received chemotherapy immediately before targeted therapy		XX (XX.X%)
Number of patients having received chemotherapy immediately after targeted therapy		XX (XX.X%)
Number of patients having received chemotherapy immediately after a somatostatin analoganalog (as main treatment)		XX (XX.X%)
Number of patients having received chemotherapy immediately after a somatostatin analoganalog (as main treatment)		XX (XX.X%)
Number of patients having received chemotherapy as 1st line, then targeted therapy as 2nd line (at inclusion)		XX (XX.X%)
Number of patients having received alkylating chemotherapy at least once after inclusion		XX (XX.X%)
Number of alkylating chemotherapies received after inclusion	N	XX
	Missing data Mean (SD) Mean [Min; Max] [Q1; Q3]	XX XX.XX (X.XX) XX.X [XX.X; XX.X] [XX.X; XX.X]
	0 1 2 3 >3	XX (XX.X%) XX (XX.X%) XX (XX.X%) XX (XX.X%) XX (XX.X%)

Programmer note: add as a footnote the list of patients whose start date for their last main treatment line falls after the date of the last visit.

